6.3 Patient Involvement

Development of the study protocol and the final trial design has been supported by patient representatives as well as leading HG researches from Amsterdam. Patient representatives from the Danish and English patient organisations have provided valuable input to the protocol, specifically on outcome measures, feasibility of the study and ethical considerations.

6.4 Trial Schedule

Planned first subject first visit	February 2019
Planned last subject randomised	February 2021
Planned last subject last visit:	February 2021
End of trial	October 2021

7. Trial population

The trial population will consist of pregnant women with HG both out-patient and hospitalised patients.

If a patient at the time of referral to hospital is in a condition where treatment with intravenous antiemetics (ondansetron or other) is indicated, such treatment will be initiated. If and when the patient's clinical condition improves sufficiently for a transfer to orally administered antiemetics, the patient can then be enrolled in the trial.

Subjects meeting all of the inclusion criteria listed and none of the exclusion criteria will be considered eligible for the trial.

7.1 Inclusion criteria

- Written informed consent obtained before any trial related procedures are performed
- Female age >18 years
- Pregnant woman with gestational age between 5+0 and 11+6
- Nausea and vomiting without other obvious reason
- PUQE-24 score ≥ 13 OR
PUQE-24 score ≥ 7 AND
 - 1. weight loss $>5\%$ of pre-pregnancy weight and/or
 - 2. hospitalisation due to nausea and vomiting of pregnancy

Compliance with this criterion on any given day within 3 days prior to screening (possibly not compliant with this criterion on day of randomization)

- Singleton pregnancy
- The subject must be willing and able to comply with trial protocol

7.2 Exclusion criteria

- Molar pregnancy, multiple gestation or non-vital pregnancy
- Nausea and vomiting of other aetiology than NVP

CONFIDENTIAL

- Allergic to selective 5-HT3-receptor antagonists
- Ongoing treatment with antidepressant medication
- Pre-existing diagnosis of chronic kidney disease, diabetes type 1 or 2, significant cardiac disease (incl. long QT syndrome), epilepsy, HIV. In case of other pre-existing conditions subjects might be excluded based on individual assessment by an MD
- Elevated liver enzymes (ALAT/ASAT >150 U/l)
- Elevated creatinine (>100 µmol/l)
- ECG showing long QT-syndrome (QTc >460msek)
- Weekly alcohol intake >2 units of alcohol
- Not able to take medicine orally
- Not able to understand spoken and/or written Danish
- Participation in another investigational drug trial within current pregnancy

7.3 Recruiting

Eligible subjects, either out-patient or hospitalised, will be identified by medical professionals (MD, nurse or midwife) involved in their treatment. The subjects will be asked if they are interested in hearing more about the trial. If they accept they will be informed about the trial by either that same medical professional or specific trial personnel. Consent from an eligible subject must be obtained before any transfer of information on the subject from a medical professional involved in the treatment to trial personnel.

7.4 Discontinuation

Subjects will be informed about the possibility of discontinuing the trial at any time. We will encourage the subjects to inform the investigator as soon as they have decided to discontinue the trial and last administration of trial medication will be registered. In case of discontinuation we will ask the subject to indicate a reason for the discontinuation which will be registered. If the reason for discontinuation is treatment failure, time of treatment failure will be registered.

Subjects will be discontinued from the trial in case of icterus or mania or if they comply with an exclusion criterion.

Subjects may be unblinded at discontinuation if this is necessary to make clinical decisions about their future treatment. Subjects will be encouraged to fill out daily online questionnaires on possible side effects until three days after last administration of trial medication.

Birth outcome will be registered on all subjects including dropouts unless subjects withdraw consent.

Data on treatment effect (NVP symptoms) collected before discontinuation will be evaluated and dropouts will not be replaced by new subjects.

All discontinued subjects will have to return the trial medication.

8. Randomisation, treatment blinding / unblinding and sample size

8.1 Randomisation

Subjects will be randomised in a 1:1:1 ratio and stratified by site.

Randomisation will be performed using REDCap to create a numbered randomisation list. After identification of an eligible patient, the subject will be assigned a randomisation number and will subsequently receive trial medication corresponding to the randomisation number.

CONFIDENTIAL

8.2 Blinding

A double-blind set-up will be used. Mirtazapine, ondansetron and placebo will be similar in appearance, smell and taste and will be packaged identically to maintain the treatment blind.

Information on type of trial medication corresponding to each randomisation number will be kept by Glostrup Apotek and thus will not be accessible to trial personnel involved in the conduct of the trial during the intervention. Neither the sponsor, the subject, nor the investigational site staff will know which treatment the subject is receiving.

If a subject desires to continue the IMP after the intervention, the randomisation code for that particular subject can be broken. Thus, for unblinded subjects data collected after unblinding (side effects and AEs 0-3 days after the intervention and birth outcome) will not be blinded for the subjects or the clinicians, but the statistician will remain blinded.

The randomisation code for a particular subject can be broken during the intervention in a medical emergency or if knowledge of the IMP is necessary for the optimal treatment of the subject.

To break the randomisation code the investigational staff must call Glostrup Apotek which is available at all times of day and night.

Whenever a randomisation code is broken, the person breaking the randomisation code must record the time, date and reason as well as his/her initials in the source documents. The sponsor and investigator must be notified immediately after randomisation code break if this happens because of an emergency during the intervention. No matter the reason for unblinding, the subject must be discontinued from the trial (side effects and AEs 0-3 days after the intervention and birth outcome will still be collected).

8.3 Sample Size

The trial is dimensioned to find a difference of 2 in PUQE-24 score change from baseline to Day 2 (short term) and/or from baseline to Day 14(+/-1)(long term) between the mirtazapine group and the placebo group with 80% power based on a standard deviation (SD) of change of PUQE-24 score of 3, a type 1 error rate of 2,5% and 25% drop-out. The reason for the 2,5% type 1 error rate is that we want to test 2 hypotheses; effect of mirtazapine versus placebo short and long term on HG.

Thus, we will have to include 57 subjects in each of the 3 groups, which we round up to 60 subjects, equivalent of 180 subjects all together.

An SD of 3 is a conservative estimate based on the placebo-controlled trial with doxylamine-pyridoxine(39).

9. Trial Products

9.1 Administration of Trial Products

Each subject will be randomly assigned to receive mirtazapine (IMP1), ondansetron (IMP2) or placebo. Please refer to figure 1 on page 17 for a visual on the trial design.

Trial medication will be provided by Glostrup Apotek in accordance with GMP. IMP1, IMP2 and placebo will be similar in appearance, smell and taste due to the IMPs being encapsulated in gelatine. In the placebo group the medication will be an empty gelatine capsule.

At Visit 1 on Day 0 each subject will receive two containers with sufficient medication for 10 days. One container will be labelled 'Morning' and one will be labelled 'Bedtime' to be administered orally in the morning and at bedtime for the first week (until Visit 2 on Day 7(+/-1)). Administration will start at bedtime of Day 0.

Thus, during the first week of intervention there will be two administrations of trial medication daily.

At Visit 2, two new containers with sufficient medication for 10 days will be administered. If dosage increase is not desired administration will proceed unchanged.

If a dosage increase is desired the number of daily administrations will go from two to four. One container will then be labelled 'Morning, noon and afternoon' and will be administered orally in the morning, at noon and late afternoon or early evening. The other container labelled 'Bedtime' will be administered only at bedtime.

In case a subject vomits within 45 minutes after administration of trial medication the subject will have to administer a new dosage as described in the folder 'Praktisk information om forsøgsmedicinen'.

If a subject runs out of trial medication before the next visit due to extra administrations because of vomiting, the subject must contact the investigator as described in the folder 'Praktisk information om forsøgsmedicinen'.

The folder 'Praktisk information om forsøgsmedicinen' will be handed out with the trial medication. Patients are encouraged to register time of administration and possible vomiting episodes within 45 minutes after administration in the folder.

CONFIDENTIAL

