9.7 IMP Management and accountability

At each study site, there will be an IMP accountability log that will contain

- Amount received at the study site
- Date of delivery
- Expiration date
- Amount accessible at the study site
- Date and initials of the person updating the log

There will be an accountability log on subject level to ensure traceability and compliance. This log will contain

- Subject ID

CONFIDENTIAL

- Expiration date
- Amount dispensed
- Dispensed by: date and initials
- Amount returned by subject
- Excess medication received by

The subjects will be instructed to keep a log of administered IMP and rescue medication as described in the folder 'Praktisk information om forsøgsmedicinen'. They will be asked to return any unused medication. The local investigators are responsible for keeping the accountability log up to date at centre level as well as on subject level.

IMP management and accountability will be monitored by the GCP-unit throughout the trial.

10. Procedures

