10.1 Visit Schedule

Visit ID	Procedures to be performed at the visit
Screening Visit Day -2-0	Obtain written informed consent for the trial before any other trial procedures are performed Assess compliance with inclusion and exclusion criteria Obtain demographic data Record medical history Record use of relevant previous medications and concomitant medication Record PUQE-24 score Record pre-pregnancy weight Measure weight Measure height Measure vital signs Perform physical examination Perform ultrasound scan to confirm gestational age and singleton pregnancy, if there is no record of such in the medical journal from within 4 four weeks prior to visit Collect blood samples Record ECG to rule out long QT-syndrome Schedule date for next visit.
Visit 1 (Randomisation) Day 0 Baseline values recorded	Re-assess compliance with inclusion and exclusion criteria Record changes to concomitant medication Record PUQE-24 score Record nausea VAS Record number of daily vomiting Record EQ-5D, NVPQOL, HELP and modified PSQI Record possible patient consideration of termination of pregnancy Measure weight Measure vital signs Collect blood samples Randomise the subject Instruct the subject on how to use the IMP Dispense IMP, rescue medication and B-kombin to the subject (sufficient medication for 10 days) Schedule date for next visit
Visit 2 Day 7	Re-assess compliance with inclusion and exclusion criteria Record changes to concomitant medication and including rescue medication Record PUQE-24 score Record nausea VAS Record number of daily vomiting Record EQ-5D, NVPQOL, HELP and modified PSQI

CONFIDENTIAL

Visit ID	Procedures to be performed at the visit
	Record patient satisfaction with treatment VAS Record possible patient consideration of termination of pregnancy Record sick leave Record possible hospitalization Record possible administration of i.v. fluids Record side effects Assess AEs occurring since the last visit Record use of rescue medication Record desire for dosage increase Measure weight Measure vital signs Record ECG Collect blood samples Collect used IMP and rescue medication and perform drug accountability and compliance check Dispense IMP, rescue medication and B-kombin to the subject (sufficient medication for 10 days) Schedule date for next visit

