- Change in PUQE-24 score on short and long term in the ondansetron group versus the placebo group.
- Change in PUQE-24 score on short and long term in the mirtazapine group versus the ondansetron group.

CONFIDENTIAL

- Area under the curve for PUQE-24 score day 1-14.
- PUQE well-being score.
- Number of daily vomiting episodes.
- Nausea VAS.
- NVPQOL (health-related quality of life for nausea and vomiting during pregnancy).
- HELP (hyperemesis level prediction).
- EQ-5D (a measure of health-related quality of life).
- 7 days PSQI (Pittsburg Sleep Quality Index)
- Patient satisfaction with treatment VAS.
- Patient consideration of termination of pregnancy.
- Occurrence of treatment failure.
- Use of rescue medication.
- Request for dosage increase.
- Days on sick leave.
- Amount of treatments with i.v.-fluids.
- Days of hospitalization.
- Weight change.
- Request for continuation of trial medication after end of intervention.
- Birth outcome (birth weight, gestational age, APGAR, umbilical cord pH, placenta weight, sex, hospitalizations on neonatal ward during the first month, congenital malformations).

Trial medication:

All trial medication will be provided by Glostrup Apotek in accordance with GMP. The investigational medicinal products (IMPs) will be similar in regard to appearance, smell and taste due to the IMPs being encapsulated in gelatine. Each subject will be given two containers one labelled 'Daytime' and one labelled 'Bedtime' to be administered orally in the morning and before bedtime for 14 days.

In the mirtazapine group, the 'Daytime' medication will contain placebo and the 'Bedtime' medication will contain mirtazapine 15 mg.

In the ondansetron group both the 'Daytime' and the 'Bedtime' medication will contain ondansetron 8 mg.

In the placebo group both the 'Daytime' and the 'Bedtime' medication will contain placebo.

Increase in dosage will be possible on Day 7(+/-1) in case of insufficient effect of medication during the first week.

Trial schedule:

Planned first subject first visit:	January 2019
Planned last subject randomised:	July 2020
Planned last subject last visit:	July 2020
End of trial:	January 2021

2. Flowchart

	Screening Day -2-0	Visit 1 Randomisation Day 0	Online questionnaire Day 1-14	Visit 2 Day 7(+/-1)	Visit 3 Day 14(+/-1)	Day 15-17	Postpartum
Informed Consent	x						
In- and Exclusion criteria	x	x		x	x		
Demography	x						
Medical History	x						
Previous and concomitant medication	x						

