6.3 Blinding

A double-blind set-up will be used. Mirtazapine, ondansetron and the matching placebo will be similar in appearance and will be packaged identically to maintain the treatment blind. Neither the sponsor, the subject, nor the investigational site staff will know which treatment the subject is receiving.

In case a subject desires to continue the IMP after the intervention, the randomization code for that particular subject can be broken. Thus, for unblinded subjects data collected after unblinding (AEs 0-5 days after the intervention and birth outcome) will not be blinded for the subjects or the clinicians, but the statistician will remain blinded.

Furthermore, the randomisation code for a particular subject can be broken during the intervention in a medical emergency or if knowledge of the IMP is necessary for the optimal treatment of the subject. Whenever a randomisation code is broken, the person breaking the randomisation code must record the time, date and reason as well as his/her initials in the source documents. The sponsor and investigator must be notified immediately after randomisation code break if this happens because of an emergency during the intervention. No matter the reason for unblinding the subject must be discontinued from the trial (birth outcome will still be collected).

CONFIDENTIAL

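### Protocol 9.1 gives the placebo group an empty capsule, and nothing in either document requires it to match the filled active capsules in weight, feel or sound: an avoidable risk to the blind.

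*Protocol*

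**What the plan says.** Protocol 9.1 describes the placebo product in one sentence: "In the placebo group the medication will be an empty gelatine capsule". The sentence before it bases the match on the capsule shell: "IMP1, IMP2 and placebo will be similar in appearance, smell and taste due to the IMPs being encapsulated in gelatine". The Protocol synopsis makes the same claim, as does the SAP synopsis: "The investigational medicinal products (IMPs) will be similar in regard to appearance, smell and taste due to the IMPs being encapsulated in gelatine".

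The blinding sections set the standard to be met. Protocol 8.2 has: "Mirtazapine, ondansetron and placebo will be similar in appearance, smell and taste and will be packaged identically to maintain the treatment blind". SAP 6.3 is shorter: "Mirtazapine, ondansetron and the matching placebo will be similar in appearance and will be packaged identically to maintain the treatment blind". The aim in Protocol 8.2 is: "Neither the sponsor, the subject, nor the investigational site staff will know which treatment the subject is receiving".

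Elsewhere the placebo goes by other names. Protocol 6.1, 9.2 and 9.4 and SAP 6.1 call it an oral tablet; SAP 6.3 calls it a matching placebo. For the mirtazapine arm, Protocol 9.2 says that the Morning container holds placebo and the Bedtime container mirtazapine, without saying what that placebo capsule contains.

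On returns, Protocol 9.7 says of the subjects: "They will be asked to return any unused medication". The Visit 2 and Visit 3 lists in Protocol 10.1 include: "Collect used IMP and rescue medication and perform drug accountability and compliance check".

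**The concern.** A gelatine shell can equalise look, smell and taste. It cannot by itself make an empty capsule weigh, feel or sound like one with a drug inside. The plan therefore specifies a physical difference between placebo and active product, and its own matching criteria would not detect it.

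The blind matters here because the primary endpoint is self-reported: Protocol 6.1 and 10.16 have patients complete PUQE-24 online. Protocol 3.2 notes a considerable placebo effect in trials of other treatments for nausea and vomiting of pregnancy. That is not evidence about these drugs in hyperemesis, but it shows that the authors take expectation seriously. Several secondary endpoints also rest on the patient's own judgement, among them satisfaction, requests for a dosage increase, and treatment failure, which Protocol 10.17 defines by her decision to stop for insufficient relief.

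Neither document plans a check of whether the blind held, so a failure could go unnoticed.

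**Working it through.** No figure in the plan is in dispute, so the check is a comparison of the passages, followed by who handles what and when.

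**1. What the matching statements cover**

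| Place | Attributes named | Weight, feel or sound | Fill |
|---|---|---|---|
| Protocol synopsis and 9.1 | appearance, smell, taste | no | none for placebo group (empty) |
| Protocol 8.2 | appearance, smell, taste, packaging | no | not mentioned |
| SAP synopsis | appearance, smell, taste | no | not mentioned |
| SAP 6.3 | appearance, packaging | no | not mentioned |

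A pharmacy that followed 9.1 to the letter would supply empty placebo capsules and still satisfy every row.

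**2. What each arm holds in week 1** (Protocol 9.2 to 9.4)

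| Arm | Morning | Bedtime | Contents of the two containers |
|---|---|---|---|
| Mirtazapine | placebo (fill not stated) | mirtazapine 15 mg | different |
| Ondansetron | ondansetron 8 mg | ondansetron 8 mg | same |
| Placebo | placebo (empty, 9.1) | placebo (empty, 9.1) | same |

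Only the mirtazapine arm has two different contents. It is 60 of the 120 patients planned for the primary comparison (60 + 60, Protocol 8.3).

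**3. Patient route (conditional).** Assume one capsule per dose.
- Supply on Day 0: 2 containers × 10 days = 20 capsules.
- First dose is at bedtime on Day 0 (Protocol 9.1). Doses due before the Day 2 score: Day 0 bedtime, Day 1 morning, Day 1 bedtime = 3, or 4 if the Day 2 morning dose comes first.

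If the mirtazapine arm's Morning placebo is empty, a patient in that arm can compare an empty with a filled capsule before both coprimary assessments. If that placebo is filled and matched, this comparison does not exist.

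**4. Staff route.** Assume full adherence and no re-dosing after vomiting.
- Used by a Visit 2 on Day k: 1 + 2 × (k − 1), plus 1 if that morning's dose has been taken.
- Day 6: 11–12 used, 20 − 12 to 20 − 11 = 8–9 returned.
- Day 7: 13–14 used, 6–7 returned.
- Day 8: 15–16 used, 4–5 returned.

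Staff thus receive empty capsules from the placebo group and filled ones from the active arms, whatever the mirtazapine arm's placebo contains. For patients still in the trial this starts at Visit 2, after the Day 2 score. No stated step leads from a staff member's suspicion to the patient's own online PUQE-24 entry.

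These counts show who has capsules in hand and when. They do not show that the capsules can be told apart.

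**The case against.** The strongest reply is that nothing shows the capsules to be distinguishable. Capsule opacity, the fill of the active capsules and any product specification held by the pharmacy are not described, and supply is under GMP. A protocol's silence on weight and sound does not prove that they are uncontrolled. This stands as a limit on the claim: the documents show a risk and not a broken blind. It does not remove the point, because 9.1 is not silent on the fill of the placebo group's capsule; it says empty. If the word was shorthand for no active drug, the sentence still needs correcting.

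A reader might infer that patients on mirtazapine will identify their treatment from the two containers. The documents do not support that. Protocol 9.1 limits the empty capsule to the placebo group, and 9.2 says only placebo, or placebo oral tablet. The patient would also need to know enough of the design to interpret a difference between containers, and the consent text is not available to this review.

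A reader might equally infer that accountability checks would bias the primary endpoint. That also goes too far: staff do not score PUQE-24, counting returns does not necessarily mean examining capsules, and the route cannot reach the Day 2 endpoint.

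Two further objections carry weight. PUQE-24, although self-reported, asks for hours of nausea and counts of vomiting and retching in fixed bands, which leaves less room for expectation than a global rating. And side effects may reveal the arm anyway: Protocol 9.2 lists sedation, somnolence and increased appetite for mirtazapine at more than 10%. But drug effects cannot be designed out, whereas an empty capsule can.

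**Conclusion.** The point holds as an avoidable weakness in the blind. It rests on the explicit wording of Protocol 9.1 and on the absence of weight, feel, sound or fill from every matching statement in both documents.

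Its size cannot be stated. The documents give no basis for the probability that anyone would be unblinded or for the size and direction of any effect on PUQE-24. A reader might want to translate the risk into a false-positive rate or a loss of power, but any such number would describe an assumed bias from an arbitrary cause and not this capsule.

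The staff route needs no assumption about the mirtazapine arm's placebo, but its link to the primary endpoint is not established. The patient route would precede both coprimary assessments, but it exists only if the mirtazapine arm's Morning placebo is empty too. The inconsistent naming of the placebo leaves that open and is itself a reason to amend the text. This is a cheap improvement worth making; it does not show that the trial's result would be unsound.

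**What to change.** - **Protocol 9.1:** replace the empty capsule with an identical gelatine capsule containing an inert fill, and say that this applies to every placebo dose in every arm, including the mirtazapine arm.
- **Protocol 9.1 and 8.2:** require active and placebo capsules to be similar in weight, feel and sound as well as appearance, smell and taste. The active capsules include both mirtazapine strengths and ondansetron.
- **Protocol 6.1, 9.1, 9.2 and 9.4; SAP 6.1 and 6.3:** reconcile the three descriptions of the placebo (empty gelatine capsule, oral tablet, matching placebo) into one term.

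The cost is pharmacy filling work and an update of the product documentation. This is likely minor, but the documents give no manufacturing details from which to quantify it. Dose, visits, questionnaires and sample size do not change. The amendment closes one route to unblinding; it does not secure the blind against recognisable side effects.
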